4.4 Regression Analysis

1. Effects of treatment on county-level outcomes (Covid-19 vaccinations, content engagement, other behavioral or survey outcomes):

- (a) Main analysis: $Y_{ct} = \alpha_t + \gamma_c + \beta_1 Direct_{ct} + \beta_2 Friends_{ct} + \beta_3 Gossips_{ct} + \delta Y_{c0} + \epsilon_{ct}$
 - Y_{c0} is a baseline measure of the outcome
 - *Direct, Friends* and *Gossips* are the three treatment groups. Treatment is assigned at the county level. We may also pool together friends and gossips, or all three treatment groups in some specifications.
- (b) Heterogeneous effects of treatment: $Y_{ct} = \alpha_t + \gamma_c + \beta_1 X_{ct} + \beta_2 Treat_{ct} + \beta_3 Treat_{ct}X_{ct} + \epsilon_{ct}$
 - We plan to explore heterogeneity along the following dimensions:
 - Political leaning (red/blue) – this was a stratification variable
 - Baseline vaccination rates – we stratified on baseline population percentage with 1st dose of vaccine
 - Percentage white/non-white
 - Relevant vaccine mandates
 - Prior/baseline infection rates
 - Urban vs rural

We may look at heterogeneity in specifications which consider each treatment group separately, as well as specifications which pool together treatment groups.

- (c) Distributional impacts using quantile regression
 - We may repeat the exercises above with quantile regressions.
- (d) Do people who visit the study website from different treatment groups click on different content (e.g. vaccine-related videos)? For example, do website visitors respond to myth vs fact videos differentially by treatment group?

2. Comparing the efficacy of myth- vs question-based messaging

- (a) $Y_{ict} = \alpha_t + \gamma_c + \beta \mathbb{1}(Myth_{ict}) + \epsilon_{ict}$
 - Y_{ict} stands for engagement-related outcomes such as video views, website visits, and video shares
 - We will examine myth- vs question-based messaging at both the Facebook ad level and at the website level. (The videos vary in whether they are myth- or question-based both in the Facebook ads which are served to users, as well as in the videos which are visible to website visitors.)

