2.5 Treatment Assignment

The counties in the study sample were randomized into three treatment groups and a control group: 1) a “direct” messaging group (T1), 2) a “friends” messaging group (T2), 3) a “gossips” messaging group (T3), and 4) a control group which did not receive any Facebook ads from us.

Randomization was conducted at the county level. County-level randomization was stratified by three characteristics: 1) state, 2) political leaning (according to 2020 election results), and 3) baseline vaccination rates. For political leaning, counties were divided into below- and above- median GOP vote in the 2020 presidential election. For baseline vaccination rates, counties were divided into above- and below-median percentage of the population that had received the 1st dose of Covid-19 vaccine.

After stratifying on these three variables, strata were adjusted so that no stratum was smaller than 9 counties. Strata with fewer than nine counties were dissolved by baseline percentage of population with first dose of vaccine. For the three states (South Carolina, Michigan, and Wyoming) where this does not result in strata that have at least nine counties, we dissolve instead by baseline GOP vote share. In total, this left us with 47 strata.

Exceptions: County-level GOP votes were not available for Alaska, and so this stratification variable was used for the other 18 states in the sample only.

Out of the 1,397 counties which fit the eligibility criteria for the experiment, we assigned 468 counties to the control group, 310 counties to T1 (“direct” messaging) treatment, 309 counties to T2 (“friends” messaging), and 310 counties to T3 (“gossips” messaging).

3. Hypotheses

Primary hypotheses:

1. Do the ads affect the new Covid-19 vaccinations in treated areas?
 - 1st dose of vaccine
 - 2nd dose/completed vaccination
 - Booster shots
2. Which type of messaging (“direct,” “friends,” or “gossips”) is most effective at driving engagement and shares of vaccine-related content, as well as new vaccinations?

3. Is myth- or question-based messaging more effective at eliciting engagement with vaccine-related content?

Secondary hypotheses:

4. Do the ads affect Covid-19 cases, hospitalizations, or symptoms in treated areas?
5. Do the ads spill over onto other areas that are connected to the treatment counties?
 - Behavioral spillovers: new vaccinations
 - Covid-19 case, hospitalization, symptom impacts

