4.1 Primary Outcomes

1. **Covid-19 vaccinations:** this includes 1st doses, 2nd doses/completed vaccination, and booster shots when available. These data are available at the county level.

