4.2 Secondary Outcomes

1. **Engagement with content related to Covid-19:** this includes website views, video views, and social media shares of vaccine-related videos and messaging, disaggregated at the county or treatment group level.
2. **Other Covid-19 outcomes:** depending on data availability, this will include Covid-19 symptoms, cases, hospitalizations, and deaths. The investigators do not expect the study to be well-powered on this outcome.
3. **Other survey outcomes:** if available, we may assess outcomes on vaccine hesitancy according to surveys. The investigators do not expect the study to be well-powered on this outcome.
4. **Other behavioral outcomes:** we may also study whether the treatments have an effect on movement and travel, as well as school or other institutional closures. The investigators do not expect the study to be well-powered on this outcome.

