4.7 Inference

For our core analyses, we will use heteroskedasticity-robust standard errors. We will check for additional statistical robustness following the approaches outlined in Section 5 of the Supplementary Appendix of [this paper](#).

5. Funding and Human Subjects Review

Facebook is supplying sufficient ad credits to fund the campaign. The IRB at MIT is serving as the primary institution of record and has entered into a reliance agreement with Harvard, Stanford, Massachusetts General Hospital, and Yale.

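### Hypothesis 2 asks which message works best, but the visible plan gives no formal between-arm test, and model 1(a) as written cannot supply the ranking, least of all for engagement

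*Combined protocol and SAP*

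**What the plan says.** Section 3 lists as primary the question of which message "is most effective at driving engagement and shares of vaccine-related content, as well as new vaccinations". The outcome sections rank these differently. Section 4.1 makes vaccination the only primary outcome, and "this includes 1st doses, 2nd doses/completed vaccination, and booster shots when available". Section 4.2 places engagement among the secondary outcomes, and "this includes website views, video views, and social media shares of vaccine-related videos and messaging, disaggregated at the county or treatment group level".

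Section 4.4, item 1(a), is headed "Effects of treatment on county-level outcomes (Covid-19 vaccinations, content engagement, other behavioral or survey outcomes". Its model has a time effect, a county effect `gamma_c`, one indicator for each of Direct, Friends and Gossips, and a baseline value `Y_c0` of the same outcome. Control is the omitted group. On combining arms, the plan says only: "We may also pool together friends and gossips, or all three treatment groups in some specifications". Item 1(d) asks whether website visitors from different arms click on different content, but gives no model or test.

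Section 4.7 names heteroskedasticity-robust standard errors and adds: "We will check for additional statistical robustness following the approaches outlined in Section 5 of the Supplementary Appendix of" an outside paper. Section 2.5 describes "a control group which did not receive any Facebook ads from us". Section 2.4 says that the website was built for the study, and Section 2.3 dates the start of the campaigns to 22 December 2021.

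**The concern.** Which message is best is a question about differences between treated arms. The stated coefficients compare each arm with no ads. Three estimates always produce a top-ranked arm, even when the messages are equal. A reader who sees one arm significant against control and another not may take that as a difference between messages. If the contrast, the pooling and the error rule are chosen after the data are seen, the answer is open to selection. A pre-analysis plan exists to close off those choices.

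Model 1(a) also has an identification problem. A county's assigned arm and its baseline value do not change over time, and a county effect absorbs anything that does not change over time.

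For engagement, the control group and the baseline add little. Control counties get no ads, and a site built for the study probably has no informative earlier traffic. At stake is whether a hypothesis that the plan calls primary has a defined analysis.

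**Working it through.** **Inputs.** Sections 2.1 and 2.5 give 468 control, 310 Direct, 309 Friends and 310 Gossips counties. The sum is 1,397, which equals 1,402 − 5, so the plan's count reproduces. Treated counties: 310 + 309 + 310 = 929. Strata: 47. The plan states no alpha, power, effect size or county SD. Two-sided 5% is assumed throughout, and power is varied.

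**1. Identification of model 1(a).** Take a toy panel of 40 counties and 5 periods: 5 time columns, 39 county columns, 3 arm terms and 1 baseline term, 48 columns in all.

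| Rows available | Rank without arm terms and `Y_c0` | Rank with arm terms | Rank with arm terms and `Y_c0` |
|---|---|---|---|
| Post-launch only | 44 | 44 | 44 |
| Pre- and post-launch | 44 | 47 | 47 |

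On post-launch rows alone, no arm coefficient is identified. With pre-launch rows all three are, but `Y_c0` is still redundant. This is algebra and holds for vaccinations as well as engagement.

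**2. What the control group adds for engagement.** With control engagement set to zero and a Poisson mean of 3 in treated counties (illustrative), the arm-versus-control t statistics are 28 to 30. Friends minus Direct is 0.219 (SE 0.140) both with and without the control counties. So the stated tests show that ads produce engagement, and control contributes nothing to the comparison of messages.

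**3. Arm-versus-control tests when the messages are equal.** Give all three arms the same true effect, d = (1.96 + z_power) × √(1/468 + 1/310) = (1.96 + z_power) × 0.0732 SD. At 80% power d = 2.80 × 0.0732 = 0.205 SD. Share of simulated trials in which some but not all arms are significant:

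| Assumed power per arm | 20% | 50% | 80% | 90% |
|---|---|---|---|---|
| Arms disagree | 37% | 55% | 37% | 22% |

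**4. Between-arm tests when the messages are equal, one outcome.** Normal theory at the planned counts:
- any of three ungated pairwise tests: 12.2%
- the same plus pooled Friends and Gossips versus Direct: 12.8%
- joint equality test (2 df): 5.0%
- pairwise tests only after the joint test rejects: 5.0%

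With skewed county engagement (log-normal, CV 0.5 to 3 assumed, 929 counties, 47 strata of near-equal size, HC2 errors), the ungated figure is 9.8% to 12.2% and the gated figure 4.3% to 5.8%.

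**5. Across outcomes.** The 5% is per outcome. For independent tests, three outcomes give 1 − 0.95³ = 14% and six give 1 − 0.95⁶ = 26%. Correlated outcomes would give less.

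**6. What the joint test can detect.** Residual df = 929 − 47 − 2 = 880. Noncentrality for 80% power with F(2, 880) is 9.67. If one arm differs: √(9.67 / (310 × 619 / 929)) = √(9.67 / 206.6) = 0.216 SD. If the arms are evenly spaced, the range is about √(9.67 / (310/2)) = 0.250 SD. Without a county SD, this cannot be turned into views or shares.

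**7. Several rows per county.** In a simulated county panel with equal arms, unclustered robust errors rejected equality in 21% and 38% of runs at assumed serial correlations of 0.5 and 0.8, against 5% with clustering by county. For a 2-df test the false rejection rate is 0.05^(1/D), where D is the factor by which the variance is understated. The two figures therefore correspond to D = 2.996/1.561 = 1.9 and 2.996/0.968 = 3.1. The size depends on the number of rows per county and their correlation, which the plan does not give.

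**The case against.** The strongest reply is that the differences follow directly from model 1(a) wherever its coefficients are identified, so nothing prevents the comparison. That is true. What is missing is the choice of contrast, pooling and error rule.

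Item 1(d) does ask a between-arm question, so the plan is not silent. It covers only what visitors click on and names no test. The appendix cited in Section 4.7 may contain a multiplicity method; the point is limited to what the document shows.

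A reader might infer that the no-ad control group distorts the ranking of messages. Step 2 shows that it does not.

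A reader might also infer that an engagement baseline is impossible. The document never says that there was no earlier traffic; that the baseline is uninformative is an inference from a purpose-built site and the launch date. Nor is engagement confined to the site: Section 4.2 includes social media shares, and for the myth comparison Section 4.4 looks "at both the Facebook ad level and at the website level".

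Finally, the 22% to 55% disagreement might be read as an error rate of the plan. It is not, because the plan states no rule that infers a message difference from it. Optional pooling by itself matters little: 12.2% becomes 12.8%.

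**Conclusion.** The point stands as a gap in prespecification together with a model that does not fit the question. Hypothesis 2 can be answered from the planned data, but the visible plan does not say how, and model 1(a) as written cannot give the ranking on post-launch rows. For engagement with pre-launch zeros, the stated tests show mainly that ads produce engagement.

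The size is about 12% false differences per outcome with three ungated pairwise tests, against about 5% with gating, given equal messages and a two-sided 5% level. The disagreement figures in step 3 rest on assumed power and only illustrate why arm-versus-control tests cannot rank messages. The clustering figures rest on assumed serial correlation. Near-zero control engagement is also an inference; any visits from control counties would be spillover, not a no-treatment comparison.

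The change should be made. The documents do not support the stronger reading that the design cannot compare the messages.

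**What to change.** 1. **Engagement.** Compare arms among the 929 treated counties, with one row per county, a denominator fixed in advance (for example adults, since the ads target users aged 18 and older), randomisation-stratum effects and robust errors, and without `gamma_c` or `Y_c0`. Set in advance how share-driven visits are credited, for example to the arm of the originating county through the sharing chain, since diffusion is what Friends and Gossips aim at. Report control-county visits under spillovers as well. For website outcomes attributed to county, use the period in which county was recorded (Section 4.3), the same for all arms.
2. **Test.** Test Direct = Friends = Gossips jointly, and test the pairwise differences only if the joint test rejects. Name one lead engagement and one lead vaccination outcome, or adjust across outcomes. State whether the engagement ranking is primary or secondary.
3. **Vaccinations.** Keep the control group and apply the same equality test in an identified model. Use either one row per county with `Y_c0` and stratum effects and no `gamma_c`, or a panel with pre-launch rows and `gamma_c` and no `Y_c0`. Cluster errors by county whenever counties have several rows, in place of the unclustered robust errors of Section 4.7.

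The cost is plan wording and minor extra code. Control counties leave the engagement model. Measures held only by treatment group cannot get the county-level test and can be reported only descriptively.

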4.6 Controls

For all regressions, we will use machine learning techniques to select the controls. Potential controls include: baseline Covid-19 vaccination or case rates, state fixed effects, county-level demographic information from the census, county- or state-level vaccination policies, and many other attributes.

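### Section 4.4 defines neither gamma_c nor t: read as county effects, gamma_c absorbs Y_c0 in 1(a), and on a pre+post panel a fixed moderator's own trend loads onto the interaction in 1(b)

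*Combined protocol and SAP*

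**What the plan says.** Section 4.4, item 1, covers "Effects of treatment on county-level outcomes (Covid-19 vaccinations, content engagement, other behavioral or survey outcomes". Model 1(a), labelled the main analysis, begins "Y_{ct} = \alpha_t + \gamma_c + \beta_1 Direct_{ct" and goes on to the other two arms, a term delta × Y_c0 and an error. The notes under it explain only Y_c0 ("Y_{c0} is a baseline measure of the outcome") and the arms ("Treatment is assigned at the county level").

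Model 1(b) has the same alpha_t and gamma_c, then "\beta_1 X_{ct} + \beta_2 Treat_{ct} + \beta_3 Treat_{ct}X_{ct", with no Y_c0 and no X-by-time term. Of the six moderators listed there, five are fixed for a county or naturally read so: political leaning, baseline vaccination, percentage white, prior infection and urban/rural. Vaccine mandates may change over time.

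No section says what gamma_c is, how long a period is, or whether periods before launch enter. Section 2.3 gives only the campaign dates, 22 December 2021 to 27 January 2022. Section 4.6 leaves controls to machine learning: "Potential controls include: baseline Covid-19 vaccination or case rates, state fixed effects, county-level demographic information from the census", among others. Section 4.7 makes heteroskedasticity-robust errors the core choice and refers to a linked appendix for further checks.

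**The concern.** The index c is the county, since outcomes and assignment are both at county level, so gamma_c reads most naturally as a county fixed effect. On that reading 1(a) contains a term that cannot be estimated. The reader cannot tell whether the vaccination result will be a difference-in-differences or a baseline-adjusted post-launch comparison.

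In 1(b) the county effects also absorb the main effect of any fixed moderator. The equation then has nowhere to put a difference in vaccination trend between, say, red and blue counties except the interaction. Randomisation does not protect against this, because the fault is a missing term in the model and not an imbalance between arms. At stake is a reported difference in effect between county types that does not exist, together with a misstated effect in the reference group.

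The undefined t also decides whether the section 4.7 errors are adequate, because a county that contributes several rows may have correlated errors.

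**Working it through.** **Inputs from the plan.** Arms of 468, 310, 309 and 310 counties (section 2.5), total 1,397 = 1,402 − 5 (section 2.1); 47 strata (section 2.5). The plan states no figure that this point disputes.

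**Assumptions.** Binary X with P(X=1) = 0.5, noise SD 1, 5 pre and 5 post periods unless stated, and all values of g, rho and AR(1).

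**1. What 1(a) can estimate.** Rank of the three arm terms plus Y_c0, after removing the fixed effects:

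| gamma_c | Periods | Coefficients estimable |
|---|---|---|
| County | Pre and post | 3 of 4 (delta lost) |
| County | Post only, treatment constant after launch | 0 of 4 |
| 47 strata | Post only | 4 of 4 |

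**2. Cost to the main estimate on a pre+post panel.** With one pre and one post value of equal variance s² and correlation rho, a change score has variance 2s²(1 − rho) and a baseline-adjusted value s²(1 − rho²). The ratio is 2/(1 + rho): 2/1.9 = 1.05 at rho 0.9 and 2/1.99 = 1.005 at rho 0.99.

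**3. Bias in 1(b) with county effects, a pre+post panel and fixed X.** In first differences the model regresses the change on a constant, Treat and Treat × X. Let the true mean change be a + gX + b2·Treat + b3·Treat·X.

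- Controls share one fitted mean: a + g·P(X=1).
- Treated, X=0: a + b2. The fitted beta_2 is therefore b2 − g·P(X=1).
- Treated, X=1: a + g + b2 + b3. The fitted beta_3 is therefore b3 + g.

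With b2 = 0.5, b3 = 0 and g = 0.5, the formulas give 0.5 − 0.25 = 0.25 and 0.50. Simulated means (beta_2, beta_3), 400 runs per g:

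| g | As printed | With X-by-time terms |
|---|---|---|
| 0 | 0.501, −0.001 | 0.501, −0.004 |
| 0.25 | 0.376, 0.246 | 0.500, 0.005 |
| 0.5 | 0.247, 0.500 | 0.498, 0.005 |
| 1 | −0.009, 1.001 | 0.494, 0.006 |

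Rejection of a true zero interaction at nominal 5%, county-clustered, AR(1) 0.5: 5.5%, 15.5%, 42.8% and 99.5% at g = 0, 0.05, 0.1 and 0.25 as printed; 4.3% to 6.3% with X-by-time terms. These rates depend on the panel. With independent errors and g = 0.1, they were 17% for one pre and one post period and 66% for four pre and six post.

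**4. Readings without the bias.** Strata effects on post-launch data gave beta_2 of 0.49 to 0.52 and beta_3 of −0.02 to 0.01 at every g from 0 to 1. Reading X_ct as X-by-post gave 0.495 to 0.500 and 0.004 to 0.007.

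**5. Standard errors.** False-positive rate for the Direct coefficient in 1(a), county effects, 1,000 runs:

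| AR(1) | Heteroskedasticity-robust | County-clustered |
|---|---|---|
| 0 | 4.0% | 4.1% |
| 0.5 | 17.7% | 4.6% |
| 0.8 | 31.1% | 5.8% |
| 0.95 | 32.3% | 5.7% |

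Runs that also covered five post-launch periods without county effects gave 19% to 41%, against about 4% to 7% clustered. With one pre and one post period at AR(1) 0.5, the two kinds of error gave identical rejection for the interaction: 6.6% as printed and 4.4% with X-by-post.

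**The case against.** The best defence is that the text does not force county effects. Under them, Y_c0, the main effect of a fixed X, and the baseline rates, state effects and demographics offered in section 4.6 would all be absorbed if entered in levels. That so many printed terms would be redundant suggests a looser meaning such as strata, state or random effects. In 1(b) both Treat and X carry the subscript ct; if Treat_ct is assignment-by-post, X_ct may be X-by-post, and the missing term is then already there. Selected controls might also repair 1(b). Heterogeneity is only exploratory ("We plan to explore heterogeneity along the following dimensions"), and no document gives g. The error inflation rests on an assumed panel, and the linked appendix may deal with it.

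Much of this stands and limits the point. The bias in 1(b) is conditional, and its size is unknown. But each defence supplies a definition that the plan does not give. X is described only through county attributes, nothing says that it is interacted with time, and section 4.6 names no X-by-time candidate. The appendix is offered for additional checks and not as the core inference.

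A reader might also infer that 1(a) cannot handle website engagement, because the site was built for the study and has no earlier measure. That is minor: pre-launch counts are structurally zero, a constant Y_c0 simply drops out, and the arm effects remain estimable with strata effects, or with county effects on a pre+post panel.

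**Conclusion.** The point holds in conditional form and should be fixed. What is certain is that gamma_c and t are undefined and that Y_c0 is redundant if gamma_c is a county fixed effect. What is conditional is the bias in 1(b): it needs county effects, pre- and post-launch periods, a moderator fixed over time, and a non-zero g. It then equals g in beta_3 and −g·P(X=1) in beta_2. The understated errors need serial correlation and either more than two periods or, without county effects, more than one post-launch period.

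Three stronger conclusions are tempting and not supported.

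- **The vaccination effect in 1(a) is biased.** It is not: on a pre+post panel the arm effects are a valid difference-in-differences, and the precision loss is about 5% of variance at rho 0.9.
- **The arm effects cannot be estimated at all.** That needs county effects on post-launch data alone with treatment constant after launch, and nothing shows that this panel is intended.
- **1(b), or the section 4.7 errors, fail on any reading.** Strata or state effects with post-launch data, or X-by-post, remove the 1(b) bias; one pre and one post period removes the error inflation.

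Every g, rho and AR(1) value is an assumption.

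**What to change.** In section 4.4, define gamma_c and t, and state one of two forms.

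- **(i) Post-launch data.** Replace gamma_c with effects for the 47 randomisation strata. Put Y_c0, the last value before 22 December 2021, in both models and keep X_c as a main effect wherever it is used. Omit Y_c0 where no pre-launch measure exists. Where the moderator is itself the baseline outcome, enter it once.
- **(ii) Pre+post panel.** Keep county effects, drop Y_c0, and add X-by-time terms to 1(b).

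In either form, amend section 4.7 so that errors are clustered by county whenever a county contributes more than one row.

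The cost is a few lines of wording and no new data. Under (ii), X-by-time terms lose precision on beta_3 when X has no trend of its own: its simulated SD rose from 0.043 to 0.071 with independent errors, and from 0.057 to 0.097 at AR(1) 0.5. Under (i), adding Y_c0 to 1(b) should gain precision: leaving it out multiplies the variance of beta_3 by 1/(1 − rho²), which is 1/0.75 = 1.33 at an assumed within-stratum rho of 0.5 and 1/0.36 = 2.78 at 0.8.

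### If γ_c in exploratory model 1(b) is a county effect, the Treat-by-X coefficient absorbs any secular change in the outcome gap by X, because the equation has no X-by-period term

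*Combined protocol and SAP*

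**What the plan says.** Section 4.4, 1(b) gives the heterogeneity model as "Y_{ct} = \alpha_t + \gamma_c + \beta_1 X_{ct} + \beta_2 Treat_{ct} + \beta_3 Treat_{ct}X_{ct} + \epsilon_{ct". It is exploratory: "We plan to explore heterogeneity along the following dimensions". Six dimensions follow. Two were used in the stratification: "Political leaning (red/blue) – this was a stratification variable" and "Baseline vaccination rates – we stratified on baseline population percentage with 1st dose of vaccine". The others are racial composition, vaccine mandates, prior or baseline infection, and urban versus rural. Pooled and separate-arm versions are both foreseen: "We may look at heterogeneity in specifications which consider each treatment group separately, as well as specifications which pool together treatment groups".

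The plan does not define α_t, γ_c or the values Treat takes over t. For 1(b) it states neither a pre-launch window nor whether Y is cumulative coverage or doses per period. Model 1(a) carries the same α_t and γ_c together with a baseline term, explained as "Y_{c0} is a baseline measure of the outcome". Section 4.6 adds: "For all regressions, we will use machine learning techniques to select the controls". Its list begins "Potential controls include: baseline Covid-19 vaccination or case rates, state fixed effects, county-level demographic information from the census" and ends open, with policies and other attributes. It names no product of X with time.

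**The concern.** Whether the ads worked differently in, say, red and blue counties should be judged by comparing the red–blue difference among treated counties with the same difference among control counties. Under the county-effect reading, the printed model does not make that comparison. It has no term through which control counties' outcomes can move differently by X, so a divergence that would have happened without any ads is credited to the Treat-by-X product.

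Randomization does not protect against this. Treatment is independent of X, but the omitted X-by-post term is correlated with Treat × X × post by construction. The error can run either way: it can create an interaction where there is none, or hide a real one.

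**Working it through.** **Inputs from the documents.** Model terms: section 4.4, 1(b). Allocation: 468 control and 310 + 309 + 310 = 929 treated counties, 1,397 in all (sections 2.1 and 2.5). Launch December 22, 2021, planned end January 27, 2022 (section 2.3). The plan gives no power or effect figure for 1(b), so there is none to reproduce.

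**Assumptions, not in the documents.** X binary with mean 0.5; θ from 0 to 1.0; SD of a county's before–after change 1, 2 or 4, in the same units as θ.

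**Step 1, identification.** If γ_c is a county effect, a Treat variable constant over time is collinear with it. Treat must therefore vary over t; take Treat = T_c × post_t. A modifier fixed per county is also collinear with γ_c, so β₁X drops out. In a noise-free panel of 60 counties and 10 weeks, the printed design has 72 columns and rank 71.

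**Step 2, differencing.** In a balanced panel the fit is equivalent to regressing each county's before–after change on T and T × X. Suppose the truth is

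ΔY = a + θX + b₂T + b₃TX + e,

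while the model fits only ΔY = a + β₂T + β₃TX. Controls supply one mean, a + θE[X]. Treated counties supply their own intercept, a + b₂, and slope, b₃ + θ. Hence

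- β₃ = b₃ + θ
- β₂ = b₂ − θE[X].

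**Step 3, numerical check with zero ad effect.**

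- Cumulative coverage, gap moving −0.1 point per week, 5 weeks before and 5 after: the mean week number rises from 3 to 8, so θ = −0.1 × 5 = −0.50. The fit gives β₃ = −0.50 and β₂ = +0.25. With X-by-period terms (80 columns, rank 80) both are 0.
- New doses per week with a steady gap: θ = 0, and both coefficients are 0.
- New doses with the gap moving from −0.1 to −0.2: β₃ = −0.10, β₂ = +0.05.
- Cumulative coverage, Treat switched off after the campaign, 5 weeks before, 5 on and 5 after: untreated mean week (3 + 13)/2 = 8, treated mean 8, so β₃ = 0. With 2 weeks after instead of 5, the untreated mean is 38/7 = 5.43 and β₃ = −0.1 × 2.57 = −0.26.
- Masking, in a separate simulation: true interaction 0.3 with θ = −0.3 gives a mean estimate of −0.001 as printed and 0.294 with the X-by-post term.

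**Step 4, illustrative rejection of β₃ = 0 at nominal 5%, no ad effect (2,000 replicates per cell).** Entries are for θ = 0 / 0.1 / 0.25 / 0.5 / 1.0.

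| SD of change | Pooled, 929 treated (%) | Single arm, 310 (%) |
|---|---|---|
| 1 | 4 / 34 / 96 / 100 / 100 | 4 / 15 / 58 / 99 / 100 |
| 2 | 4 / 11 / 47 / 97 / 100 | 6 / 7 / 19 / 60 / 100 |
| 4 | 5 / 7 / 15 / 47 / 97 | 5 / 7 / 9 / 19 / 59 |

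With X-by-post terms, rejection is 4.4–6.6% pooled and 4.4–6.1% single arm in all 15 cells. The Gossips-minus-Direct interaction contrast, fitted as printed, rejects 4.2–5.9%, because the same θ enters both arms and cancels.

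**Step 5, precision.** As printed, SE(β₃) = SD/√(n_T × 0.25). At SD 2 this is 2/√232.25 = 0.131 pooled and 2/√77.5 = 0.227 for one arm. With the extra terms the control slope is estimated and subtracted, which adds SD²/(468 × 0.25) = 4/117 = 0.0342 to the variance. The SEs become 0.227 and 0.293. The ratios are √(1397/468) = 1.73 and √(778/468) = 1.29; for Friends and Gossips pooled, √(1087/468) = 1.52.

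**Step 6, other readings.** With post-launch data only, no γ_c and constant Treat, β₁X carries the gap. With θ = 1 the mean β₃ was 0.008 and rejection 4.7%. Dropping γ_c while Treat still switches on at launch is not enough: with one period each side, the common X slope is estimated from 1,397 pre-launch and 468 post-launch control observations, so about 1397/1865 = 0.75 of θ remains (simulated 0.745).

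**The case against.** The strongest reply is that the county-effect reading is not what the plan intends. Under county effects, the baseline outcome in 1(a), the X main effect in 1(b), and the baseline, state and fixed census controls in section 4.6 would all be redundant. Each has a purpose in a post-launch, baseline-adjusted model, where there is no bias. No switch-on rule is printed; section 2.3 gives a launch date but does not connect it to the model. The notation may be schematic, since even political leaning carries a time subscript. Prior infection could be updated by period, and mandates may change, in which case the leakage may be partial. The control list is open, so X-by-time terms are not ruled out. Hypothesis 1 concerns new vaccinations, for which a steady gap does no harm.

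Much of this stands. It makes the point conditional and limits its weight. It does not remove it: c is most naturally the county, county effects force Treat to vary over time, and an open list handled by machine learning does not commit to the term that is needed.

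A reader might infer that the planned red/blue comparison will be biased, or that the main vaccination results are at risk. The documents support neither. They do not fix the reading or give θ, and model 1(a) has no X interaction. None of the five hypotheses in section 3 concerns modification by county characteristics.

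**Conclusion.** Wrong as written under the county-effect reading; minor, because the analysis is exploratory. What is established is the pass-through: θ enters β₃ in full, and −θE[X] enters β₂, in pooled and arm-versus-control versions with a modifier fixed per county. This rests on γ_c being a county effect, Treat switching over time, and no X-by-period control being selected.

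The size of θ is unknown. For cumulative coverage it is non-zero whenever county types gain vaccinations at different rates, apart from special symmetric windows. For new doses per period it is non-zero only if the gap changes. The rejection rates show how detection depends on assumed values; they do not show that the problem is material in this trial. Engagement outcomes with no pre-launch series are also outside the point.

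**What to change.** In 1(b), define γ_c, Treat (including its value after January 27, 2022), the form of Y and the pre-launch window. Then choose one of two routes.

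1. If county effects are intended, always include X_c-by-period terms, with X fixed at its pre-launch value and not left to machine-learning selection, in both pooled and arm-by-arm versions.
2. Otherwise drop γ_c and fit post-launch data with constant Treat, X, Treat × X, the baseline outcome and strata. This is a different estimator, close to what the plan's baseline and control terms suggest. In simulation at SD 2 and θ from 0 to 1.0, with the 47 strata, it rejected 4.6–6.0% pooled and 4.8–5.3% for a single arm.

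Neither route needs new data. The first costs one set of regressors and the precision loss in step 5: the SE of β₃ is 1.73 times larger pooled, 1.52 times for Friends and Gossips pooled, and 1.29 times arm by arm. That is the price of bringing the 468 controls into the interaction. The second has similar SEs at SD 2 (0.231 pooled, 0.298 single arm).
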